9.7.1.6.2 SECONDARY EFFICACY ANALYSES

The secondary analyses will be performed only if the primary analysis is significant. The treatment effect for elenbecestat (E2609) 50 mg/day versus placebo, for each secondary efficacy endpoint, will be tested using a sequential testing procedure at a significance level of 2-sided $\alpha = 0.05$, ie, any test will start only if the test with higher hierarchical order is significant. The final hierarchical order will be specified later in the statistical analysis plan before database lock.

Time to worsening of CDR scores by 24 months will be analyzed on the FAS using Cox regression model for treatment effect adjusting for randomization stratification factors. Time to worsening of a CDR score is defined as time from randomization to worsening of the CDR score (ie, the first worsening in 2 consecutive scheduled visits). For subjects whose CDR scores have not worsened by the end of study, the time to worsening of the CDR score will be censored at the date of last CDR assessment for these subjects.

Time to conversion to dementia for subjects who were not clinically staged as dementia at Baseline based on clinical diagnosis will be analyzed on the FAS using Cox regression model for treatment effect adjusting for randomization stratification factors. Proportion of subjects with dementia diagnosis at 24 months will be estimated using Kaplan—Meier method based on time to conversion to dementia based on clinical diagnosis. Time to conversion to dementia for subjects who were not clinically staged as dementia at Baseline based on clinical diagnosis is defined as time from randomization to conversion to dementia based on clinical diagnosis. For subjects without clinical dementia by the end of study, the time to conversion to dementia based on clinical diagnosis will be censored at the date of last dementia diagnosis.

The rate of change over time (mean slope) based on change from baseline in the CDR-SB will be analyzed using linear mixed effects (LME) models for multivariate normal data derived from a random coefficient model (slope analysis), where the mean slope in each group depends on a continuous assessment time. The LME model will include baseline CDR-SB, randomization stratification variables, assessment time, and treatment group-by-assessment time.

The other continuous secondary efficacy endpoints as defined above will be analyzed using the same MMRM model as the primary efficacy analysis to compare elenbecestat (E2609) 50 mg per day versus placebo on the FAS, using baseline value corresponding to the response variable in the model.

The relationship between clinical changes at 24 months (CDR-SB, ADAS-cog₁₄, MMSE, and FAQ) and changes in each of the biomarkers (amyloid PET, tau PET, CSF A β (1-42), t-tau, p-tau, vMRI, and fMRI) at 24 months, will be evaluated using an ANCOVA model. (revised per Amendments 01, 04, and 05) Changes in clinical scales at 24 months will be the response variables and either continuous or categorical change of biomarkers will be independent variables. The ANCOVA model will also include baseline value for clinical scale as a covariate, randomization stratification variables, treatment group as factors, and other terms as appropriate.

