9.7.1.6.1 PRIMARY EFFICACY ANALYSIS

The primary analysis will be based on an intent to treat philosophy without regard to adherence to treatment. The primary analysis of the change from baseline in CDR-SB at 24 months will be performed to compare elenbecestat (E2609) 50 mg per day versus placebo using a linear mixed effects model for repeated measures (MMRM) on the FAS. The MMRM model will include baseline CDR-SB as a covariate, with treatment group, visit, randomization stratification variables (ie, region [7 levels], clinical dementia [yes, no], and concurrent AD medication use at randomization (Visit 2) [yes, no]), and treatment group-by-visit interaction as fixed effects. (revised per Amendments 01 and 02) An unstructured covariance matrix will be employed to model the covariance of within subject effect; if MMRM fails to converge then a covariance structure with fewer parameters from the following list will be employed according to the prespecified order in the list until the MMRM converges. The list of covariance structure will include Heterogeneous Toeplitz, Toeplitz, Heterogeneous Compound Symmetry, and Compound Symmetry. This primary analysis will include all observed post baseline data of the change from baseline in CDR-SB without imputation of missing values. The treatment effect for elenbecestat (E2609) versus placebo will be compared at 24 months based on MMRM model. The LS means and difference in LS means between elenbecestat (E2609) treatment group and placebo, and corresponding 95% CI will be presented.

The null hypothesis is that there is no difference in the mean change from baseline in CDR-SB at 24 months between elenbecestat (E2609) 50 mg per day and placebo. The corresponding alternative hypothesis is that there is a difference in the mean change from baseline in CDR-SB at 24 months between elenbecestat (E2609) 50 mg per day and placebo.

The primary analysis will be repeated to minimize the impact of change in concomitant AD medications where efficacy data after initiation of new AD medications and increase of current AD medications will be censored.

The following sensitivity analysis will be conducted to evaluate the impact of missing data: the primary endpoint will be analyzed using ANCOVA after multiple imputation. The ANCOVA model will include baseline CDR-SB as a covariate, with treatment group and randomization stratification variables as factors.

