9.1.2.1 Treatment Period

During Visit 2, the following assessments will be completed before the subject receives their first dose of study drug: MMSE, CDR, ADAS-cog₁₄, FAQ, and NPI-10. (revised per Amendment 01) These assessments will provide baseline measurements for the study. For any given subject, every effort should be made to ensure that the CDR rater remains unchanged throughout the study. (revised per Amendment 04) Inclusion and exclusion

criteria will again be reviewed together with concomitant medications and assessment of AEs. A single 12-lead ECG will be conducted. All ECG recordings will be evaluated by a central reader. (revised per Amendment 01) The Columbia-Suicide Severity Rating Scale (C-SSRS) will also be administered. A baseline routine physical examination with dermatologic review, vital signs measurements, clinical laboratory testing (including viral characterization), urinalysis using urine dipstick, and a urine pregnancy test (females of child-bearing potential only), will be performed. Additional blood samples will be taken for PD/exploratory biomarkers and immunologic assessments. (revised per Amendment 04) Some of the immunologic assessment blood sample will be used to prepare isolated peripheral blood mononuclear cells (PBMCs) which will be stored for testing as required. (revised per Amendment 03) The results of some of the immunologic assessments will be provided to the DSMB for periodic review during the study. (revised per Amendment 01) Whilst there is no prescribed order in which the assessments at each visit are to be performed, the subject component of the cognitive, functional and quality of life assessments are to be performed in the morning whenever possible, or consistently at the same time of the day and ideally should be completed before the more invasive procedures (eg, physical examination, ECG, blood draw).

Subjects will be randomized at Visit 2 (Day 1) to receive elenbecestat (E2609) 50 mg per day or placebo administered orally QD in the morning with or without food. Subjects will be encouraged to stay at the site for observation for at least 30 minutes following their first dose of study drug. The duration of this observation period can be extended at the Investigator's discretion, eg, if warranted by medical history or concomitant medication. (revised per Amendment 04) Double-blinding to study drug will be in effect throughout the Treatment Period.

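### Both secondary Cox models adjust only for the randomisation strata and leave out baseline CDR-SB: valid tests, but a cheap gain in efficiency is forgone

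*Protocol*

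**What the plan says.** Section 9.7.1.6.2 states that the CDR-worsening endpoint "by 24 months will be analyzed on the FAS using Cox regression model for treatment effect adjusting for randomization stratification factors". For conversion, the analysis "based on clinical diagnosis will be analyzed on the FAS using Cox regression model for treatment effect adjusting for randomization stratification factors". Section 9.7.1.6.1 lists the stratification variables: "region [7 levels], clinical dementia [yes, no], and concurrent AD medication use at randomization (Visit 2) [yes, no". The same Cox wording stands in the synopsis and in the other copies of the section.

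The neighbouring models go further. For the primary endpoint, "The MMRM model will include baseline CDR-SB as a covariate", in addition to the strata, and the multiple-imputation ANCOVA does the same. For the slope analysis, in the same section as the Cox models, "The LME model will include baseline CDR-SB, randomization stratification variables, assessment time". The remaining continuous secondary endpoints each use their own baseline value.

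The covariate is available. At Visit 2, "the following assessments will be completed before the subject receives their first dose of study drug: MMSE, CDR", and Section 9.1.2.1 adds: "These assessments will provide baseline measurements for the study". The FAS definition in Section 9.7.1.2 requires a baseline value of the primary efficacy measure. Both time-to-event endpoints belong to the sequential two-sided 0.05 procedure.

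**The concern.** Subjects must have a global CDR of 0.5 at Screening, and the protocol's example of worsening is a rise of at least 0.5 on that scale. Section 9.2.1 derives the global score and CDR-SB from the same six domains. How far a subject already is along the CDR-SB scale at entry should therefore help to predict when the next global level is reached. The strata capture this only through a yes/no dementia flag.

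The conversion analysis covers only subjects not staged as having dementia at Baseline. The dementia flag then takes a single value and adjusts for nothing. AD medication use is at most an indirect proxy for severity.

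Omitting a prognostic covariate from a Cox model costs power and moves the estimated hazard ratio towards 1 relative to the effect conditional on that covariate. In a sequential procedure, a test that misses also stops whatever is ranked below it.

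**Working it through.** **The plan's own figure.** The protocol gives no event count, hazard ratio or power for either Cox analysis, so the only figure to reproduce is the sample size in Section 9.7.2. Inputs: placebo change 1.75, SD 2.05, 25% reduction, 30% dropout, 90% power, two-sided 0.05.

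- Difference = 0.25 × 1.75 = 0.4375.
- n per arm = 2 × 2.05² × (1.960 + 1.282)² / 0.4375² ≈ 462.
- 462 / 0.70 = 660 per arm, 1320 in total, against 1330 stated. With 665 × 0.7 = 465.5 evaluable per arm, power is 90.2%. The stated size reproduces.

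**Simulation A: proportional hazards with a prognostic baseline.** The hazard is λ·exp(log 0.75 × treatment + log h × x), where x is a standardised baseline and h its hazard ratio per SD.

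- From the documents: 24 months, 1:1 allocation, 30% dropout, N = 1330 for worsening. For conversion N = 0.75 × 1330 ≈ 998, because subjects with dementia are capped at about 25%.
- Assumed, not in the documents: conditional hazard ratio 0.75, placebo 24-month event rate 30% or 50%, h from 1.0 to 2.5.
- Strata were not simulated, so h should be read as the strength remaining within strata.
- 600 trials per setting; Monte Carlo error about 1 to 2 points of power.

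Power (%) without → with the baseline covariate:

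| h per SD | Worsening, 30% events | Worsening, 50% | Conversion, 30% | Conversion, 50% |
|---|---|---|---|---|
| 1.0 | 70.5 → 70.7 | 90.3 → 90.0 | 54.3 → 54.3 | 78.8 → 78.5 |
| 1.3 | 69.3 → 69.7 | 91.3 → 92.7 | 54.7 → 54.3 | 78.7 → 81.2 |
| 1.6 | 66.7 → 70.8 | 89.3 → 90.8 | 53.2 → 56.8 | 77.3 → 81.2 |
| 2.0 | 64.8 → 70.7 | 82.5 → 90.0 | 52.7 → 59.8 | 67.3 → 78.2 |
| 2.5 | 58.5 → 71.5 | 76.8 → 90.7 | 47.8 → 56.8 | 66.2 → 83.0 |

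With the covariate the hazard ratio is recovered at 0.746 to 0.756 throughout. Without it, the estimate is 0.757 to 0.762 at h = 1.6, 0.763 to 0.779 at h = 2.0 and 0.777 to 0.789 at h = 2.5.

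**Simulation B: CDR-SB trajectories.** This uses the plan's mean, SD, effect, dropout and 3-monthly visits. Assumed: baseline mean 2.2, baseline SD 0.5 to 1.1, correlation of baseline with later decline −0.2 to 0.3, visit noise SD 0.8, and an event when CDR-SB reaches 4.5 (at two consecutive visits for worsening, at the first such visit for conversion). There were 400 replicates per scenario (Monte Carlo SE of each power about 0.025), with both models fitted to the same data.

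| Baseline SD, correlation | Worsening | Conversion |
|---|---|---|
| 0.5, 0 | 0.72 → 0.74 | 0.63 → 0.67 |
| 0.8, 0 | 0.68 → 0.74 | 0.55 → 0.62 |
| 1.1, 0 | 0.63 → 0.69 | 0.46 → 0.59 |
| 1.1, 0.3 | 0.55 → 0.68 | 0.42 → 0.58 |
| 0.8, −0.2 | 0.69 → 0.71 | 0.62 → 0.66 |

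From these rounded powers the gain is 2 to 13 points for worsening and 4 to 16 for conversion. Under the null, rejection was 0.028 with strata only and 0.040 with baseline added, so neither model inflates type I error.

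**Loosening the conversion proxy.** When each subject's diagnostic threshold varies around 4.5 with SD 0, 0.5, 1.0 and 1.5 (again assumed; correlation 0, 300 to 400 replicates), the conversion gain is about 9, 5, 4 and 1 points at baseline SD 0.8, and about 11, 9, 8 and 1 points at baseline SD 1.1.

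**The case against.** The strongest reply is that nothing here is an error. A Cox model adjusted for the randomisation strata is standard and its test is valid. That stands.

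A reader might infer that the planned hazard ratios are biased towards 1. The documents do not support that reading. The shift is non-collapsibility: the strata-adjusted hazard ratio is a different, less conditional quantity, and it is estimated properly.

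A reader might also take the larger power losses as what this trial should expect. Neither the prognostic strength nor the spread of baseline CDR-SB is given. Simulation B sets its event on the covariate's own scale, which makes the covariate strongly prognostic by construction. Section 9.2.1 describes the global score as coming from an algorithm distinct from the sum, and the protocol defines worsening only by example. Conversion is a clinician's staging, centrally reviewed and adjudicated where discrepant (Section 9.1.2.1), so a CDR-SB threshold is only a proxy and those figures sit at the upper end.

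A third tempting reading is that lost power here will block other endpoints. The hierarchy's order is deferred to the SAP, so this cannot be sized. If these two endpoints rank last, nothing else is blocked.

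The argument that the SAP could simply add the term is weaker. The protocol names the Cox covariates and, unlike the clinical–biomarker ANCOVA in the same section, leaves no room for other terms.

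**Conclusion.** The point holds as a cheap improvement, not as a flaw in validity. The protocol adjusts its continuous secondary analyses for a baseline score but not these two Cox models, gives no reason for the difference, and has the covariate in every analysed subject. The conversion model has no direct adjustment for severity.

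The amount forgone is uncertain. It is about 0 to 2 points of power if baseline CDR-SB is weakly prognostic (about 1.3 per SD) and about 14 to 17 points at the strong end (2.5 per SD with 50% events). With a conditional hazard ratio of 0.75, the less conditional estimate would be about 0.76 to 0.79 when baseline carries 1.6 to 2.5 per SD. These figures rest on assumed event rates, effect and prognostic strength. The direction does not, provided baseline CDR-SB is prognostic at all. If it is not, including it costs essentially nothing.

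**What to change.** In both Cox sentences of Section 9.7.1.6.2, and in the matching synopsis text, insert *baseline CDR-SB and* before the reference to the randomisation strata. Prespecify this before unblinding, since adding it later would look data-driven. Keep the strata-only model as a sensitivity analysis. The constant dementia factor in the conversion model drops out of the fit by itself, so removing it from the text is tidying and changes no result.

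The cost is one covariate in two models, with no new data. The downside is one of interpretation: the primary hazard ratio for each endpoint becomes conditional on baseline CDR-SB as well as on the strata, and should be described that way.

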9.7.1.6.3 EXPLORATORY EFFICACY ANALYSES

Time to change of concomitant AD treatment will be analyzed similarly to that for time to conversion to dementia based on clinical diagnosis. Time to change of concomitant AD treatment is defined as time from randomization to the first dose increase and/or initiation of treatment with AChEI or memantine after randomization. For subjects without any change of concomitant AD treatment by the end of study, the time to change of concomitant AD treatment will be censored at the date of last assessment of concomitant medication.

The proportion of subjects with any change of concomitant AD treatment at 24 months will be analyzed similarly to that for proportion of subjects with dementia diagnosis at 24 months.

The rate of change over time (mean slope) based on change from baseline in the NPI-10 item will be analyzed in a manner similar to that used for the rate of change over time (mean slope) based on change from baseline in the CDR-SB.

The analysis of the following exploratory efficacy endpoints will be performed to compare elenbecestat (E2609) versus placebo using the appropriate prespecified statistical methods including MMRM model, analysis of covariance model (ANCOVA), etc. For each exploratory efficacy endpoint, the treatment effect for elenbecestat (E2609) 50 mg per day versus placebo will be tested at a significance level of 2-sided alpha = 0.05.

- Change from baseline in NPI-10 item at 24 months
- Change from baseline in EQ-5D (subject self-reported, study partner self-reported, and subject measured by proxy) and QOL-AD (subject and study partner) at 24 months
- Change from baseline in Zarit's Burden Interview at 24 months

Additional analyses may be performed as needed.

9.7.1.7 Pharmacokinetic, Pharmacodynamic, Pharmacogenomic, and Other Biomarker Analyses

9.7.1.7.1 PHARMACOKINETIC ANALYSES

Safety Analysis sets will be used for individual elenbecestat (E2609) plasma and CSF concentration listings. The PK Analysis Set will be used for the summaries of elenbecestat (E2609) plasma and CSF concentrations.

A population PK approach will be used to characterize the PK of elenbecestat (E2609). The effect of covariates (ie, demographics) on elenbecestat (E2609) PK will be evaluated. The PK model will be parameterized for clearance (CL) and volumes of distribution. Derived exposure parameters such as AUC will be calculated from the model using the individual posterior estimate of CL and dosing history.

9.7.1.7.2 PHARMACOKINETIC-PHARMACODYNAMIC

The PK/PD relationship between CSF biomarker levels and plasma PK parameters or CSF concentrations of elenbecestat (E2609) will be explored graphically and any emergent relationship will be explored through population PK/PD modeling. These PK parameters include maximum observed concentration (C_{max}), and $AUC_{(0-24)}$ derived from the population PK model. The PK/PD relationship between plasma PK parameters and CSF concentrations of elenbecestat (E2609) with other biomarkers may also be explored using similar methods.

Additionally, the relationship between various PK parameters (eg, C_{max}) or CSF concentrations of elenbecestat (E2609) and CDR-SB at 24 months, and the relationship between various PK exposure parameters or CSF concentrations of elenbecestat (E2609) and the change from Baseline for 24 months in ADAS-cog₁₄, and the MMSE, will be explored graphically. Any emergent relationships will be explored through population PK/PD modeling. The relationship between exposure to elenbecestat (E2609) and most frequent AEs will also be explored.

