In Study 003, a drug-drug interaction study, PK results showed that itraconazole (a potent inhibitor of cytochrome P450 [CYP] 3A4 and carboxylesterase-2 [CES2]) caused a mild increase (by approximately 70%) of the area under the concentration \times time curve (AUC) of elenbecestat (E2609). Rifampin (a potent CYP3A4 inducer) caused a mild decrease (by approximately 20%) of the AUC of elenbecestat (E2609). Donepezil (a moderate CES2 inhibitor) caused a mild increase (by approximately 20%) of the AUC of elenbecestat (E2609) when coadministered with elenbecestat (E2609) but not when dosed at least 2 hours apart from elenbecestat (E2609). Elenbecestat (E2609) (which inhibits the P-glycoprotein 1 transporter) did not affect the PK properties of digoxin. Nonclinical studies also indicated that other CYP pathways apart from CYP3A4 would not be major pathways of metabolism of elenbecestat (E2609). Based on these results, it is not considered necessary to impose restrictions during elenbecestat (E2609) treatment on the use of concomitant medications that may be CYP3A4 inhibitors or other CYP enzymes inhibitors. Similarly, it was also not considered necessary to restrict the use of concomitant medications which are inducers of CYP450 enzymes. Given the results of study 003 moderate to strong CES2 enzyme inhibitors are not permitted for a period of 5 half-lives or 7 days (whichever is longer) before randomization and until the last treatment visit.

However, simvastatin use is permitted only with once daily evening administration. Simvastatin use is recommended with night time administration as physiological studies showed that most cholesterol is synthesized when dietary intake is at its lowest. It is therefore expected that the PK interaction between elenbecestat (E2609) and simvastatin is minimized because simvastatin is thought to mainly inhibit CES2 in the intestine when E2069 will not be present as it will be administered in the morning.

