8.3 Exploratory Objectives

The exploratory objectives of this study are

- To explore the relationship between elenbecestat (E2609) exposure/PD (in CSF, plasma) with efficacy and safety endpoints (eg, immune function) as deemed appropriate (revised per Amendment 02)
- To evaluate whether elenbecestat (E2609) is superior to placebo in reducing the initiation or dose increase of other AD pharmacotherapies
- To evaluate whether elenbecestat (E2609) is superior to placebo over time and at 24 months on change on the Neuropsychiatric Inventory (NPI) 10 item
- To evaluate whether elenbecestat (E2609) is superior to placebo on overall health related quality of life (HRQoL) for subjects with EAD and study partners at 24 months as measured by the following outcome measures:
 - a. EuroQol - 5 Dimensions (EQ-5D) (5 Level version will be used)
 - b. Quality of Life in Alzheimer's Disease (QOL-AD)
- To evaluate whether elenbecestat (E2609) is superior to placebo on study partner burden for subjects with EAD at 24 months as measured by the Zarit's Burden Interview

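### The exposure-response exploration for CDR-SB uses the 24-month score, not change from baseline, so baseline severity adds noise and can confound the relation

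*Protocol*

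**What the plan says.** Section 9.7.1.7.2 of the protocol plans to relate PK parameters to clinical outcome. For the primary scale the words are "or CSF concentrations of elenbecestat (E2609) and CDR-SB at 24 months". For the other two scales the sentence continues with "the change from Baseline for 24 months in ADAS-cog₁₄, and the MMSE, will be explored graphically". The synopsis repeats this. The plots come first; then "Any emergent relationships will be explored through population PK/PD modeling". The covariates of that later model are not given.

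Exposure comes from the population PK model of Section 9.7.1.7.1: "The effect of covariates (ie, demographics) on elenbecestat (E2609) PK will be evaluated", and "Derived exposure parameters such as AUC will be calculated from the model using the individual posterior estimate of CL and dosing history".

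Section 7.1 reports an interaction with a permitted drug: "Donepezil (a moderate CES2 inhibitor) caused a mild increase (by approximately 20%) of the AUC of elenbecestat (E2609) when coadministered". The same sentence adds that no such rise was seen when the two drugs were taken at least two hours apart. Donepezil is permitted in Appendix 2, Listing 4. Study drug is taken in the morning (Section 9.4.5), and no time gap from donepezil is stated.

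By contrast, the primary endpoint (Section 9.7.1.1.1) is a change from baseline. The primary model (Section 9.7.1.6.1) contains baseline CDR-SB and concurrent Alzheimer's medication at Visit 2.

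**The concern.** Of the three clinical scales in that sentence, only the primary one is taken as a level and not as a change. A level at 24 months is baseline plus change. The baseline part was fixed before the first dose, so exposure cannot have caused it.

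Two things follow in an unadjusted plot or regression. The outcome is noisier, so a real relation is harder to see; this matters because the plot decides what goes on to modelling. And anything linked to both baseline severity and exposure can look like an exposure effect. Donepezil taken together with study drug is a candidate: it raises AUC, and its users may be further along in the disease. Higher exposure could then appear to go with a worse outcome when the drug has no such effect.

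**Working it through.** **The plan's own figure.** The effect assumed in Section 9.7.2 is 0.25 × 1.75 = 0.4375 points with SD 2.05. A two-sample comparison with 90% power at two-sided 0.05 needs 462 per arm (463 by the exact t-test). Dividing by 1 − 0.30 gives 660 to 662, against 665 stated. The sample size reproduces and is not in dispute. Completers on active drug number about 0.7 × 665 = 465.

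**Noise.** Let s be the baseline SD and r its correlation with change (both assumed). Variance of the raw score over variance of change is (s² + 2.05² + 2·r·s·2.05) / 2.05², with 2.05² = 4.2025.
- s = 0.8, r = 0: (0.64 + 4.2025) / 4.2025 = 1.15.
- s = 1.2, r = 0.4: (1.44 + 4.2025 + 1.968) / 4.2025 = 1.81.

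**Confounding.** Let a share p of subjects take donepezil with study drug, with AUC multiplied by 1.2, so λ = ln 1.2 = 0.182. Let log AUC otherwise vary with variance σ² = ln(1 + CV²). Let users differ from non-users in the outcome by δ. With no true exposure effect, the expected slope of outcome on log AUC is

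δ·λ·p(1−p) / (σ² + λ²·p(1−p)).

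For the raw score, δ is the baseline difference b plus the difference in change c. For change from baseline, δ is c alone. With p = 0.5 and CV 30%, σ² = ln 1.09 = 0.0862, so the multiplier of δ is 0.0456 / (0.0862 + 0.0083) = 0.48. With b = 1.0 and c = 0.5 the false slope is 0.72 for the raw score and 0.24 for change. Simulation gave 0.721 and 0.240.

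The simulation used 465 subjects, 2,000 runs per setting, p = 0.5, baseline SD 1.0, change SD 2.05 and no true exposure effect. The table gives the percentage of runs with a significant slope in the direction of more drug, worse outcome (nominal 2.5%). Everything except the 20%, the 2.05 and the 465 is an assumption.

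| CV of AUC | b, c (points) | Raw score | Change | Change + baseline + medication use |
|---|---|---|---|---|
| 20% | 0.5, 0 | 17.2 | 2.4 | 2.8 |
| 20% | 0.5, 0.5 | 48.5 | 20.2 | 2.4 |
| 20% | 1.0, 0.5 | 80.3 | 17.4 | 2.3 |
| 30% | 0.5, 0 | 9.2 | 2.6 | 2.6 |
| 30% | 0.5, 0.5 | 26.6 | 10.3 | 2.2 |
| 30% | 1.0, 0.5 | 50.3 | 11.2 | 2.1 |
| 50% | 0.5, 0 | 6.8 | 2.2 | 2.6 |
| 50% | 0.5, 0.5 | 13.8 | 7.8 | 2.1 |
| 50% | 1.0, 0.5 | 25.3 | 7.6 | 2.6 |

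With no AUC effect, as Section 7.1 reports for dosing at least two hours apart, λ = 0 and the formula gives a zero slope. The simulated rate for the raw score is then 2.0% to 2.8%.

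So change from baseline removes the part due to b. Where c is not zero, 8% to 20% false slopes remain, and adjustment for medication use removes those.

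**The case against.** The analysis is exploratory and graphical first. Nothing says the later model is unadjusted; its covariates are unstated and may sit in a modelling plan. If that model includes baseline CDR-SB, the raw score and the change give the same exposure coefficient. This stands. It confines the point to the stated outcome, the plots, and any model without baseline. The randomized comparison is not touched.

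Three stronger readings are tempting, and the protocol does not support them.

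- A reader might infer that the demographic covariate list in Section 9.7.1.7.1 causes the bias. It does not. AUC is taken from each subject's own posterior clearance, so a donepezil effect largely enters the exposure value whether or not donepezil is in the PK model. The confounding arises in the exposure-response step and has to be handled there.
- A reader might infer that donepezil use as such raises exposure by 20%, and that the bias rivals the design effect. With 30% to 50% users, all taking the drugs together, and AUC CV of 25% to 50%, the share of users differs by 20 to 45 percentage points between top and bottom exposure quartiles. A 1.0-point difference between users and non-users then gives 0.20 to 0.45 points. But the rise is absent at a two-hour gap, the other inputs are not in the protocol, and a contrast of extreme quartiles within one arm is not comparable with a randomized difference of 0.4375. It is an upper scenario.
- A reader might infer that the immune question is left unanswered, because the only stated exposure-safety analysis is "The relationship between exposure to elenbecestat (E2609) and most frequent AEs will also be explored". Section 8.3 gives immune function only as an example, in a discretionary objective: "with efficacy and safety endpoints (eg, immune function) as deemed appropriate". That is not a commitment that the analysis breaks.

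**Conclusion.** The point holds as a small correction to an exploratory analysis. The inconsistency in the outcome is plain on the page, and nothing in the protocol explains why CDR-SB alone is taken as a level. The variance cost of 15% to 81% rests on an assumed baseline SD of 0.8 to 1.2 and correlation of 0 to 0.4. It applies only where baseline is not adjusted for.

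The false-slope rates of 7% to 80% show that the confounding path can matter. They do not estimate its size. The share of donepezil users, how many take it with study drug, how much more impaired they are, and the between-subject spread of AUC are all absent from the protocol. If donepezil is taken at least two hours apart from study drug, this path disappears.

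**What to change.** In Section 9.7.1.7.2 and the synopsis, replace *CDR-SB at 24 months* with *change from baseline in CDR-SB at 24 months*. Add that plots will be shown by concurrent Alzheimer's medication and that any exposure-response model will include baseline CDR-SB and concurrent Alzheimer's medication.

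As a secondary change, widen *(ie, demographics)* in Section 9.7.1.7.1 to include concomitant drugs that the protocol itself reports as altering exposure, such as donepezil. This describes PK variation better but does not by itself remove the confounding.

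The cost is wording. CDR is measured at Visit 2, Alzheimer's medication at randomization is a stratification variable, and concomitant medication is reviewed at every visit. Two limits should be noted. The stratification variable does not capture medication started on study, which has to come from the concomitant medication record. And the schedule asks sites to document the time of the study drug dose on the day before PK sampling but does not mention the time of donepezil, so a yes/no variable mixes subjects who take the two together with those who do not.

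Separately, Section 9.4.7 bars moderate to strong CES2 inhibitors, while Section 7.1 calls donepezil a moderate one and Listing 4 permits it. Those passages must be reconciled.
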